### **Intervention**

A single dose of 24 mg dexamethasone iv (Dexamethasone sodium phosphate, Krka, Novo mesto, Slovenia), (6 ml), administered immediately after anesthesia induction, between 30 and 15 minutes prior to surgery.

### **Control**

A single dose of 8 mg dexamethasone iv (2 ml) with isotonic saline (4 ml), administered immediately after anesthesia induction, between 30 and 15 minutes prior to surgery.

### **Concealment**

The trial drug is contained in a syringe with 6 ml solution, transparent and identical in appearance regardless of dose, labeled with patient identification and handed to trial personnel together with the re-sealed and signed envelopes.

### **Blinding**

Participants, all healthcare providers, trial personnel, data monitoring committee, principal investigator and outcome adjudicators will be blinded throughout the study. After trial completion, the principal investigator receives the allocation sequence without intervention revealed. The intervention allocation will be revealed after performing statistical analysis and drafting the paper, including comments from all authors.

## **Time schedule**

Study expected to start: March 2017

Study expected to finish: August 2018

## **Location**

Copenhagen University Hospital, Rigshospitalet, Denmark. Department of Breast Surgery and Department of Anesthesiology, Centre of Head and Orthopaedics.

## **Participants**

Number of participants: 130, 65 in each group.

### **Inclusion criteria**

- Planned unilateral mastectomy with or without axillary dessection
- Age 18 years or older
- Able to understand Danish or English and to provide informed oral and written consent.

### **Exclusion criteria**

- Simultaneous contralateral procedure
- Breast conserving surgery
- Daily/current use of glucocorticoids or immunosuppressant medication
- Insulin-dependent diabetes
- Pregnancy or lactation
- Allergies to any of the trial drugs.

## **Procedures**

### **Inclusion and preoperative treatment**

Eligible patients are informed about the trial in relation to the pre-operative appointment.

Enrolled participants are randomized and assigned to consecutive numbers (1-130) at the time of enrollment.

On the morning of surgery, patients received acetaminophen 1 g 1-2 hours before surgery.

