## **Statistical Analysis Plan**

Categorical data are presented as numbers with percentages, and tests for significant differences between the groups are assessed with  $\chi^2$  test. Continuous data are presented as mean (95% CI) or as median with inter-quartile range or range and assessed for normal distribution with the Kolmogorov-Smirnov/Shapiro-Wilk test. Tests for significant differences between groups are performed with an independent-samples t-test or Mann-Whitney U test when appropriate. The primary outcome is evaluated using  $\chi^2$  test, and the different modalities in the discharge criterion system and length of stay (secondary outcome) are evaluated using the independent-samples Mann-Whitney U test. Need for seroma drainage, readmissions and wound infections are evaluated using  $\chi^2$  test.

All available data are used, missing data is not imputed. Data from the questionnaire on PONV and sleep is dichotomized into categories, PONV/no PONV and sleep problems/no sleep problems. A two-sided 5% significance level is chosen for the primary and secondary outcomes. To adjust for multiple comparisons in the tertiary outcome (questionnaire, 40 tests), we chose a Bonferroni corrected significance level of 0.125%.

Data analyses were conducted using SPSS for Windows, version 22 (IBM Corp., New York, USA).

Data processing is done by the investigator, who will continue to be blinded until all results are analyzed, and the abstract is written and accepted by co-authors.

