### **Randomization**

Computer generated, double-blind block randomization. Allocation ratio 1:1, block sizes (2,4,6,8) randomly vary and unknown to study personnel.

The allocation sequence with intervention details (24 mg or 8 mg dexamethasone) will be concealed in consecutively numbered (1-130), opaque envelopes by two other investigators not otherwise involved in the trial. Before sealing, 20 % of the envelopes are randomly controlled.

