#### **Sample size**

After modification of our ERAS protocol introducing high-dose glucocorticoids (125 mg methylprednisolone (equivalent to 24 mg dexamethasone) we observed a 30 % to 10 % decrease in PACU referral after mastectomy. To test the isolated effect of the increased glucocorticoid dosage in a well-implemented ERAS protocol, we chose to compare 24 vs 8 mg dexamethasone. Considering the observed 20 % absolute (66% relative) reduction in need for PACU transfer clinically relevant, a sample size of 130 patients (65 in each group) was calculated ([www.sealedenvelope.com](http://www.sealedenvelope.com)) with a two-sided 5 % significance level, a power of 80 % and an anticipated 10 % exclusion rate.

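### Does randomising at enrolment, rather than on the day of surgery, waste part of the 130-patient sample?

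*Combined protocol and SAP*

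**What the plan says.** Patients hear about the trial around the pre-operative appointment. Under Inclusion and preoperative treatment, "Enrolled participants are randomized and assigned to consecutive numbers (1-130) at the time of enrollment". The drug comes later: the Intervention section has it "administered immediately after anesthesia induction, between 30 and 15 minutes prior to surgery", and the Control section gives the same timing.

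The Participants section states "Number of participants: 130, 65 in each group", and the Randomization section has the allocations "concealed in consecutively numbered (1-130), opaque envelopes by two other investigators not otherwise involved in the trial". So 130 is the number randomised. The Sample size section obtains it from 30% versus 10% PACU transfer at a two-sided 5% level, with "a power of 80 % and an anticipated 10 % exclusion rate".

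The syringe is prepared for the individual patient. Under Concealment it is "labeled with patient identification and handed to trial personnel together with the re-sealed and signed envelopes". The Statistical Analysis Plan covers incomplete data in one sentence: "All available data are used, missing data is not imputed". It names no analysis population. The documents give neither the expected causes of exclusion nor the interval from enrolment to surgery.

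**The concern.** Between enrolment and theatre a patient may withdraw, have surgery cancelled, or be switched to breast-conserving or bilateral surgery. Both of those operations are listed under Exclusion criteria, the latter as "Simultaneous contralateral procedure". Such a patient has used a number but has received neither dose and has no primary outcome. With 130 numbers and 10% budgeted as exclusions, about 13 randomised patients are expected to drop out of the primary comparison. Nothing in the described procedures needs the allocation before the syringe is made up, so assignment on the day of surgery would seem to avoid some of these losses for little more than a change of wording.

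If that were right, precision would be at stake, together with a cleaner primary analysis that has fewer randomised patients missing from it.

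**Working it through.** **Inputs.** From Sample size: PACU transfer 30% versus 10%, two-sided 5%, 80% power, 10% exclusions. From Participants and Randomization: 130 randomised, 1:1. Not in the documents: the share *s* of the 10% that is lost before a day-of-surgery assignment. It is an assumption here, run from 0 to 1.

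**Step 1: reproduce the plan's figure.** With unpooled variance,

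n per arm = (1.960 + 0.842)² × (0.3 × 0.7 + 0.1 × 0.9) / 0.2² = 7.849 × 0.30 / 0.04 = 58.87, rounded up to 59.

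Then 59 × 1.1 = 64.9, rounded up to 65 per arm, or 130 in total, as stated. (Dividing by 0.9 instead gives 65.6, hence 66 per arm; the difference is immaterial.) The expected loss is 10% of 130 = 13, or 130 − 2 × 59 = 12 by back-calculation.

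**Step 2: hold the number consented fixed.** Let C patients consent and let 10% be lost in all.

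- Assignment at enrolment: C randomised, 0.9C evaluable.
- Assignment on the day of surgery: C(1 − 0.1s) randomised, 0.9C evaluable.

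The evaluable number does not depend on *s*. For C = 130 it is 117 under both schemes. Only the label on the loss changes:

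| s | Randomised on the day | Exclusions after randomisation | Evaluable |
|---|---|---|---|
| 0 | 130 | 13 | 117 |
| 0.5 | 123.5 | 6.5 | 117 |
| 1 | 117 | 0 | 117 |

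**Step 3: hold the number randomised at 130 instead.** Consents needed = 130 / (1 − 0.1s), and evaluable = 0.9 × consents. Power is by exact enumeration of the uncorrected chi-square test at 30% versus 10%.

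| s | Consented | Evaluable | Exact power |
|---|---|---|---|
| 0 | 130 | 117 (58/59) | 79.5% |
| 0.25 | 133.3 | 120 (60/60) | 80.2% |
| 0.5 | 136.8 | 123 (61/62) | 81.8% |
| 1 | 144.4 | 130 (65/65) | 83.2% |

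Power rises here only because more patients are consented. Randomising 144.4 at enrolment with the same 10% loss also leaves 0.9 × 144.4 = 130 evaluable, hence the same 83.2%.

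**Step 4: how far the small differences can be read.** Exact power for this test is saw-toothed: 59/59 gives 80.5%, above 60/60 at 80.2%, and 62/62 gives 81.0%, below 61/62 at 81.8%. The step from 79.5% to 80.2% is within that noise. The 117 baseline is also one patient short of the plan's 118, at which exact power is 80.5%.

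**Step 5: bias.** The Randomization, Concealment and Blinding sections describe opaque envelopes, syringes of identical volume and appearance, and blinding of participants, care providers and trial personnel. A patient lost before dosing is therefore lost without the allocation being known to those who decide.

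**The case for a change.** The strongest case for changing the plan is that every factual premise is correct, that the change is cheap, and that randomising as late as possible is good practice because it keeps the randomised set and the analysed set close together. The SAP adds to this case: it does not say how a randomised patient who never has the operation is handled, so the fewer such patients there are, the better.

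Part of this stands. Day-of-surgery assignment would reduce post-randomisation exclusions by whatever share is lost before dosing. But the protocol does not tie its 10% to that period. The allowance could equally cover losses after dosing or missing primary outcomes, and a change of operation made during surgery also falls after dosing; later assignment would prevent none of these. The change has costs as well. Someone who knows the allocation must be available on each surgical day, numbers cannot be allotted ahead, and randomising 130 could take about 133 to 144 consents.

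The missing analysis population is a real gap in wording, but it does not depend on timing. The primary outcome is the discharge score after surgery, so a patient who has no operation has no outcome under either scheme. Using all available data without imputation leads an analyst to compare those who had surgery in their allocated arms and to account for the others in the patient flow.

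**Conclusion.** No change follows. The timing is as described, and about 13 (12 by back-calculation) of 130 randomised patients are budgeted as exclusions, but the timing of assignment does not cause that loss and costs no power at a fixed number of consents. The stated 80% is already covered by the inflation from 59 to 65 per arm. The largest apparent gain, 83.2 − 79.5 = 3.7 percentage points, assumes that the whole 10% is lost before dosing and that about 14 more patients are consented; extra recruitment would bring the same gain under the present procedure.

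What remains is a trade-off between logistics and a shorter list of post-randomisation exclusions, plus a gap in the SAP that analysts would fill sensibly. A sentence saying that every randomised patient who has surgery is analysed in the allocated arm, with exclusions and reasons reported, would be harmless but would not alter the result. The conclusion assumes that the 10% total loss is the same under both timings and that concealment works as described.

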### **Anesthesia and surgery**

Participants in the trial follow standard procedures. Anesthesia is induced with propofol 2 mg/kg iv and a total dose of fentanyl 0.25 mg and maintained as total intravenous anesthesia (TIVA) with propofol (5 mg/kg/h) and remifentanyl (25µg/kg/h). The airway is handled with a laryngeal mask, or in case of obesity or reflux an endotracheal tube. Intraoperative fluid therapy is standardized with Ringers lactate, 25-30 ml/kg. Ondansetron 4 mg iv is administered 20-30 minutes prior to end of surgery. Local infiltration analgesia at the surgical site (wound infiltration) is performed intraoperatively with 20 ml bupivacaine 2.5 mg/ml by the surgeon. No routine use of drains.

### **Post-operative treatment**

Analgesics: By request, acetaminophen 1 g up to 4 times daily, ibuprofen 400 mg up to three times daily, from the evening of surgery up to and including the fifth postoperative day.. Opioids are only given in hospital, on request based on moderate or severe pain.

Antiemetics: By request, or if vomiting occurs.

### **Data management**

Before patient enrolment, the trial has to be approved by the local ethics committee, the Danish data protection agency and the Danish Medicines Agency. The trial will be registered at ClinicalTrials.gov and EudraCT and will be monitored by the Good Clinical Practice unit at a Copenhagen University Hospital.

Data belongs to sponsor.

### **Case Report Form**

Every patient enrolled will have a case report form signed by investigator. REDCap (Research Electronic Data Capture) electronic data capture tools hosted at Rigshospitalet will be used as case report form. Signed informed consent forms will be kept in a separate folder.

### **Clinical evaluations and outcome registration**

Pain (at rest) is evaluated on a numeric rating scale (NRS) by the patient, assigning pain a number between 0-10. Study personnel assign a score according to the criteria listed in appendix 1, where NRS 0 = 0 (no pain),  $0 < \text{NRS} \leq 3 = 1$  (light pain),  $3 < \text{NRS} < 7 = 2$  (moderate pain),  $\text{NRS} \geq 7 = 3$  (severe pain). If patients are not able to assign a number (e.g. due to sedation/doubt), it is accepted with a verbal rating scale (no/light/moderate/severe pain).

Nausea is evaluated by patients and assigned a score from 0 (no nausea) to 3 (severe nausea or vomiting).

Length of stay (hospital) is measured as time (hours and minutes) from start of the procedure until discharge from the ward.

Length of stay (PACU) is measured as time from arrival to PACU until the patient is deemed ready to transfer to the ward (as the actual transfer time depends on transport etc.).

The occurrence of seroma requiring drainage is recorded the first 14 postoperative days from patient records.

Readmissions for any reason, except planned procedures or oncological admissions, are collected from patient records for 30 days.

Side-effects and/or complications (any) are registered during hospital stay and up to 60 hours postoperatively. Adverse events/serious adverse events are defined according to ICH-GCP.

Patients receive a questionnaire to fill out on days 0-4. The elements of the questionnaire are:

- pain on average and at worst on the 11-point numeric rating scale (0 no pain, and 10 worst pain imaginable)
- nausea on average and at worst on the four-point numeric scale (0, none; 1, slight; 2, moderate; 3, severe) and vomiting (if any)

- use of analgesics
- feelings of sadness, restlessness or fatigue (yes/no)
- quality of sleep (good, difficulty falling asleep, frequent awakenings, no sleep)

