### **Secondary outcomes**

- Discharge score in the operating room (according to discharge criteria, Appendix 1).
- Discharge score at arrival to the ward or PACU (according to discharge criteria, Appendix 1).
- Complications/adverse events in the ward the first 24 h or until discharge.
- Length of stay (PACU/Hospital)
- Pain, self-reported in patient questionnaire. Days 0-4.
- Nausea/vomiting, self-reported in patient questionnaire. Days 0-4.
- Analgetics and antiemetics, use of, self-reported in patient questionnaire. Days 0-4.
- Quality of sleep, self-reported in patient questionnaire. Days 0-4.
- Feelings of anxiety, restlessness, fatigue, self-reported in patient questionnaire. Days 0-4.
- Seroma, requiring drainage, the first 14 postoperative days

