#### **Other collected data**

Demographical data (sex, age, height, weight, smoking status, use of alcohol, comorbidities), operative data (date and time of operation, diagnosis, duration of surgery, extent of axillary dissection, intraoperative bleeding). Type and dose of medication given by request.

All data are collected from patient record.

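### If ward discharges cluster at certain hours, hospital length of stay partly reflects when surgery began, and the unadjusted Mann-Whitney test can lose power that adjusting for start time would recover

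*Combined protocol and SAP*

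**What the plan says.** Under Clinical evaluations and outcome registration, the protocol states: "Length of stay (hospital) is measured as time (hours and minutes) from start of the procedure until discharge from the ward". The clock stops at actual departure. The next definition, for PACU stay, stops the clock when the patient is judged ready, and gives the reason: "as the actual transfer time depends on transport etc".

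The SAP says that the discharge-score modalities and "length of stay (secondary outcome) are evaluated using the independent-samples Mann-Whitney U test". It names no covariate or stratification for that test. It also states: "A two-sided 5% significance level is chosen for the primary and secondary outcomes".

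Under Other collected data, the operative items include "date and time of operation". No planned analysis uses this item, although hospital stay cannot be computed without the start time.

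**The concern.** Hospital stay is discharge clock time minus start clock time. If the ward tends to discharge at certain hours, the start time enters the outcome directly. Two patients operated on at 08:00 and 14:00 who go home together the next morning differ by six hours, and none of that difference is recovery. Randomisation balances this on average, but it stays in the outcome as noise, and an unadjusted rank test has to see the dose effect through it.

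The protocol recognises the same kind of problem for PACU stay and deals with it there. For hospital stay it has neither a readiness endpoint nor an adjustment. At stake is how a non-significant result is read: it could mean no effect on stay, or scheduling noise too large for the test.

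**Working it through.** **1. The plan's own figure.** The plan gives no SD, effect or power for length of stay. Its only sample-size figure is for PACU transfer, 30% v 10%, two-sided 5%, 80% power:

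n per arm = (1.96 + 0.8416)² × (0.3 × 0.7 + 0.1 × 0.9) / 0.2² = 7.849 × 0.30 / 0.04 = 58.9, so 59. Then 2 × 59 × 1.1 = 129.8, so 130.

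This reproduces the stated 130. The 59 per arm is used below as the evaluable number.

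**2. Inputs that the documents do not give (all assumptions).** Start times uniform over 7 h (08:00-15:00) or 4 h (08:00-12:00). All patients stay one night. Discharge is normal around 11:00 next day with SD 1, 2, 3 or 6 h. The higher dose brings actual discharge forward by one hour.

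**3. Share of variance due to start time.** A uniform spread of W hours has variance W²/12, so R² = (W²/12) / (W²/12 + SD²). For W = 7 and SD = 1 h: 4.083 / 5.083 = 0.80.

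**4. Simulated power, Mann-Whitney v rank ANCOVA** (rank of stay on arm and rank of start time). There were 1,500 trials per cell, so the simulation error is about √(0.25/1500) = 1.3 percentage points at most.

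| Discharge SD | R², starts over 7 h | Power, 7 h | R², starts over 4 h | Power, 4 h |
|---|---|---|---|---|
| 1 h | 0.80 | 61 v 100% | 0.57 | 92 v 100% |
| 2 h | 0.51 | 43 v 74% | 0.25 | 62 v 76% |
| 3 h | 0.31 | 29 v 41% | 0.13 | 38 v 44% |
| 6 h | 0.10 | 13 v 14% | 0.04 | 15 v 15% |

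Relative loss with starts over 7 h, for SD 1, 2 and 3 h: (100 − 61)/100 = 39%, (74 − 43)/74 = 42%, (41 − 29)/41 = 29%. With starts over 4 h: 8%, 18% and 14%.

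**5. Hand check, normal approximation.** Unadjusted power ≈ Φ(√(59/2) × 1/√(W²/12 + SD²) − 1.96). For W = 7 and SD = 2 h: √29.5 = 5.431 and √8.083 = 2.843, so Φ(1.910 − 1.96) = 48%. Adjusted: Φ(5.431/2 − 1.96) = Φ(0.756) = 78%. The rank-test figures of 43% and 74% lie a little below these, as expected when ranks replace a t-test on near-normal data.

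**6. Cases with no loss.** If patients leave whenever ready, at any hour, power is 74 v 74%. If the dose instead raises same-day discharge from 20% to 50% of pre-noon cases, discharged near 18:00, it is 57 v 59%.

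**7. A case that adjustment does not mend.** Suppose all patients leave at a fixed round and recovery is short (mean 6 or 9 h), with an effect of 0.52 SD of recovery time. Mann-Whitney then has 4-6% power and rank ANCOVA 4-5%. Time to readiness, had it been recorded, would give 76-80%.

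**8. Type I error.** With no effect, both tests reject in about 4-6% of simulated trials.

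**The case against.** A reader might infer from the definition that hospital stay largely measures the time of the operation and that the planned test loses most of its power. The documents do not support either statement. They contain no discharge hours, ward-round rule, range of start times, expected stay or share of same-day discharges. In the one-hour scenarios above the relative loss is 8 to 42%, and nil elsewhere. A loss of more than half of an adjusted power of 80% would need start time to explain more than roughly 60-65% of the variance in stay: at R² = 0.65, unadjusted power is 38%. Nothing shows that this trial is in that region.

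It is also fair to say that the fix does not fully match the complaint. If logistics alone set departure, the dose cannot move it, and adjusting for start time recovers nothing. The adjustment works in the intermediate case, where discharge is anchored to the clock but still responds to recovery.

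Finally, time from surgery to departure is a coherent measure of hospital use, the planned test is valid, and the trial was not sized for this outcome. These points stand, and they keep the matter minor. They do not remove the case for an adjustment that gains power in some plausible settings and costs almost none in the others.

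**Conclusion.** The point holds conditionally, as a low-cost improvement rather than an error. If ward discharge clusters at certain hours, the unadjusted test gives up power: 12 to 39 percentage points for a discharge SD of 1-3 h with starts over 7 h, and 6 to 14 points with starts over 4 h. At SD 6 h, with discharge whenever ready, or in the same-day scenario, there is no meaningful difference. All of these sizes rest on assumed start times, discharge spread and a one-hour effect. What the documents do establish is the definition, the unadjusted test, the contrast with PACU stay and the unused operation time.

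A null result should not be dismissed as scheduling noise on this evidence alone. Equally, the unadjusted analysis cannot rule that explanation out.

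**What to change.** Replace the SAP's analysis of hospital length of stay with a rank ANCOVA: rank of stay regressed on arm and rank of start time of surgery. Report the unadjusted Mann-Whitney test beside it. State which of the two is the planned analysis before the allocation is revealed.

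The cost is one SAP sentence and no new data. The downside is a slightly less familiar test for one secondary outcome. Start time is a sound covariate: patients are randomised at enrolment, and although the blinded injection comes 15 to 30 minutes before surgery, the dose has no plausible route to the operating schedule. Simple stratification by quartile of start time is not a good substitute; in the same-day scenario its power was 36%, against 57-59% for the other two tests.

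The adjustment helps only if the dose moves the actual discharge time. To cover the case where a fixed round sets departure, the sponsor could also record when each patient was ready for discharge, as is done for PACU stay. That needs one new data item and is feasible only for patients still to be observed.

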**Appendix 1. Danish Society of Anesthesiology and Intensive Care Medicine (DASAIM)- score, modified.**

## Introduction

Post-surgery, patients are traditionally observed and treated in post-anesthesia care units (PACU) until they are discharged to the ward (or directly home) assessed by standardized international discharge criteria.

The research project "Why in PACU?" (Rigshospitalet, Denmark), has since the beginning of 2016 systematically collected and analyzed procedure-related complications in the recovery phase. The complications include pain, nausea/vomiting, circulatory and respiratory problems, orthostatic intolerance and cognitive disorders. Common to all the above-mentioned post-operative problems are the possible links to the inflammatory response caused by the surgical trauma.

Glucocorticoids can in this context be central for the reduction of acute postoperative organ dysfunctions, caused by the anti-inflammatory effect. In a number of different surgical procedures, single dose, pre-operative glucocorticoids have been shown to reduce post-operative nausea and vomiting (PONV), acute pain and need of opioids as well as accelerate the convalescence.

Meta-analyses also showed that single-dose administration of glucocorticoids (methylprednisolone and dexamethasone) for surgical patients is safe as opposed to long-term treatment.

Based on positive results in other procedure-specific studies, all mastectomy patients at Rigshospitalet, have received pre-operative high-dose steroids, in the form of 24 mg dexamethasone injection since mid-2015. This has resulted in a decrease in the proportion of patients who need observation in PACU from 30 % to 10 %. The reduction is primarily due to less pain, less sedation, and lower opioid administration.

Whether this is also partly due to a "systemic effect" (Hawthorn effect) as a result of increased focus on the area cannot be excluded.

Prior to creating clinical recommendations and standards, it is required that the results be tested in a randomized, controlled, clinical trial.

The study is not placebo-controlled since the positive effects of dexamethasone 8 mg on PONV have been shown in numerous trials and is already being administered to all patients at the clinic. It would therefore not be ethically correct to withdraw from this practice.

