## **Aim**

The aim of this study is to investigate the effect of a single preoperative high-dose steroid injection on complications in the immediate postoperative phase after breast cancer surgery, with removal of the breast (mastectomy). Primary outcome is the proportion patients who require transfer to the post anesthesia care unit (PACU) and the proportion that can be transferred directly to the ward. Secondary outcomes are organ specific complications in the post anesthesia phase, pain and nausea the first 5 days, seroma and wound infection the first 14 days and readmissions the first 30 days after surgery.

The investigators hypothesize that the frequency of transfer to the PACU and organ specific complications will be lower among patients receiving high dose dexamethasone. The investigators hypothesize, that there will be no difference in wound infections, seroma or readmissions.

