## Appendix 1. Danish Society of Anesthesiology and Intensive Care Medicine (DASAIM)-score, modified.

Modifications: Pain score is numeric rating scale 0-10 instead of Visual analogue scale 0-100 mm. Oxygen saturation was measured with 2L supplementary oxygen in the operating room. Respiratory rate as category is omitted.

Patients are considered dischargeable to the ward when the score sum of all criteria is four or less and no single score is above one.

Modality	Score	Criteria
Sedation (nurse evaluation)	3	Sleeping, cannot be aroused
	2	Sleeping, aroused by physical stimuli
	1	Sleeping, aroused by verbal stimuli
	0	Fully awake
Oxygen saturation; %	3	< 85
	2	85-89
	1	90-93
	0	≥ 94
Blood pressure, systolic (mmHg) (automatic NIBP)	3	< 80
	2	80-89 or > 220
	1	90-99
	0	100-220
Heart rate; pr. min. (automatically derived from ECG)	3	< 40 or > 130
	2	40-49 or 121-130
	1	101-120
	0	50-100
Pain (at rest) Numeric Rating Scale (NRS) 0-10 (patient evaluation)	3	Severe (NRS ≥ 7)
	2	Moderate (3 ≤ NRS < 7)
	1	Light (0 < NRS < 3)
	0	None (NRS = 0)
Nausea (patient evaluation and nurse observation)	3	Severe
	2	Moderate
	1	Light
	0	None
Total	Sum

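### PACU length of stay has no value for patients who bypass the PACU, so its test appears to compare about 18 with 6 patients selected, in effect, by the primary outcome

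*Combined protocol and SAP*

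**What the plan says.** The protocol's list of secondary outcomes includes length of stay for both the PACU and the hospital. Under Clinical evaluations and outcome registration, the PACU part is defined as follows: "Length of stay (PACU) is measured as time from arrival to PACU until the patient is deemed ready to transfer to the ward". Hospital stay runs from the start of the procedure, so every patient has a value.

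The Aim section makes clear that some patients bypass the PACU; one half of the primary question is "the proportion that can be transferred directly to the ward". Appendix 1 sets the rule: a patient is "dischargeable to the ward when the score sum of all criteria is four or less and no single score is above one".

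The SAP states that "length of stay (secondary outcome) are evaluated using the independent-samples Mann-Whitney U test", at a two-sided 5% level with no multiplicity adjustment for secondary outcomes. Its missing-data rule reads "All available data are used, missing data is not imputed". Nothing in either part gives a PACU stay to a patient who bypasses the unit, names the analysis set for this outcome, or labels it as descriptive.

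**The concern.** A patient who never arrives has no start time and so, as defined, no PACU stay. Following the definition and the available-data rule literally leaves a test among PACU patients only. Two problems follow.

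- **Selection after randomisation.** Who enters the PACU is decided by the score behind the primary outcome, which is what 24 mg is expected to change. The PACU patients in the two arms are therefore not comparable groups, even in a perfectly run trial.
- **Wrong quantity.** The expected benefit is avoiding the PACU. A patient who avoids it contributes nothing to this outcome, so the largest saving in PACU time is invisible to the test.

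At stake is a secondary result, tested at an unadjusted 5%, that could show nothing, or a longer stay on 24 mg, while PACU use per patient falls sharply.

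**Working it through.** **1. The plan's own sample size.** Inputs from the Sample size section: "we observed a 30 % to 10 % decrease in PACU referral after mastectomy", two-sided 5%, power 80%, 10% exclusions. Unpooled normal approximation:

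n = (1.960 + 0.842)² × (0.3×0.7 + 0.1×0.9) / 0.2² = 58.87, so 59 per arm.

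59 × 1.10 = 64.9, so 65 per arm and 130 in total, which matches the plan. I use 59 evaluable per arm below.

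**2. Patients with a PACU stay.**
- 8 mg: 59 × 0.30 = 17.7 (95% binomial range 11 to 25)
- 24 mg: 59 × 0.10 = 5.9 (range 2 to 11)
- With all 65 per arm evaluable: 19.5 and 6.5
- Chance of 3 or fewer in the 24 mg arm, Binomial(59, 0.1): 14.6%

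**3. Precision, ignoring selection.** If stay were truly 20% shorter on 24 mg, the PACU-only test would detect it with power 17.5%, 13.2% or 10.3% at a log-SD of 0.4, 0.5 or 0.6.

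**4. Selection.** The documents give no PACU times, so this step is illustrative. Assumptions: severity S ~ N(0, 1); log stay = log 60 + h×S + normal error with SD 0.4; h = 0.5; transfer 30% on 8 mg and 10% on 24 mg; 4,000 simulated trials per mechanism.
- A: 24 mg spares only milder cases and leaves the rest unchanged (modelled as a higher transfer threshold).
- B: two thirds of would-be PACU patients are spared regardless of severity.
- C: 24 mg lowers everyone's severity by 0.757, with one fixed threshold.

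| | A | B | C |
|---|---|---|---|
| Typical median stay among PACU patients, 8 vs 24 mg (min) | 106 vs 143 | 106 vs 106 | 106 vs 98 |
| 24 mg median longer | 88.0% | 50.6% | 38.3% |
| Test significantly against 24 mg | 21.5% | 2.4% | 0.7% |
| Test significantly for 24 mg | 0.1% | 2.5% | 4.6% |
| Mean PACU minutes per patient, 8 vs 24 mg | 36.1 vs 16.0 | 36.0 vs 12.0 | 36.2 vs 11.0 |

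The last row can be checked by hand. With c the severity threshold, minutes per patient = 60 × exp(0.4²/2) × exp(h²/2) × Φ(h − c) = 73.65 × Φ(0.5 − c).
- 8 mg: c = 0.524 gives 73.65 × 0.490 = 36.1.
- A: c = 1.282 gives 73.65 × 0.217 = 16.0.
- B: 36.1 / 3 = 12.0.
- C: 16.0 × exp(−0.5 × 0.757) = 11.0.

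The reductions are 1 − 16.0/36.1 = 56%, 1 − 12.0/36.0 = 67% and 1 − 11.0/36.2 = 70%.

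**5. Sensitivity to h.** At h = 0.3, for A/B/C, 24 mg is longer in 77.7/51.2/41.5% of trials, the test is significantly against it in 11.3/2.5/1.1%, and significantly for it in 0.2/2.1/3.3%.

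**6. Zero for patients who bypass the PACU.** With h = 0.5, the Mann-Whitney test on all 59 per arm rejects in 73.7/79.4/80.2% of trials, against 80.1/80.9/80.3% for the primary chi-square without continuity correction. The two agree on significance in 93.4/97.1/97.4% of trials.

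**The case against.** **The PACU-only reading is inferred.** The SAP does not say it. If zero minutes is an observed value, the available-data rule could equally be read to include these patients. The SAP's sentence on length of stay also does not separate PACU from hospital. This stands as a limit on certainty, but it does not remove the gap: a definition that starts at arrival yields nothing to record for a patient who never arrives, and the same sentence in the SAP would settle either reading.

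**The reversal needs mechanism A.** Appendix 1 applies one fixed rule and staff are blinded. The Introduction's account of the clinic's experience, "The reduction is primarily due to less pain, less sedation, and lower opioid administration", fits C better, where a significant result against 24 mg is rare (0.7%). In A, reducing h to 0.1 brings that figure to 3.9%, near the nominal 2.5%. This stands: a reversal is possible, not shown to be likely. The failure to register the saving occurs under all three mechanisms.

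**Other outcomes cover the ground.** Hospital stay includes PACU time and is defined for everyone, and the primary outcome already measures avoidance. This limits the damage, but neither estimates PACU minutes used per patient.

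**Zero-filling mostly repeats the primary result.** True of its p-value. A test of mean minutes is also less sensitive: a Welch test rejected in 47/68/75% of trials under A/B/C. The gain is therefore an estimate with an interval, not a further significance test.

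**Low power is no defect in itself.** Agreed, since the trial was sized for the primary outcome.

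**Meeting the criteria is not the same as entering the PACU.** The primary outcome counts patients who meet the score criteria; the stay needs actual arrival. The two sets should nearly coincide, but the plan does not say that they are identical.

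**Conclusion.** The concern holds. As written, the plan most naturally leads to a test between groups formed after randomisation, about 18 against 6 patients, and it leaves out the time saved by bypassing the PACU. The counts rest on the planned 30% and 10% and on 59 evaluable per arm. The stay times and the strength of the severity effect are assumed, so the simulated percentages are illustrative.

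The firm part is that, under each mechanism examined, PACU minutes per patient fell by more than half while the PACU-only test rarely favoured 24 mg. The direction of any bias is not settled. This should be corrected, but it concerns one component of one secondary outcome; the primary analysis, the 130 patients and hospital stay stand.

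**What to change.** In the SAP:

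- Define PACU length of stay as 0 minutes for any patient who never enters the PACU, based on actual entry. State that this is an observed value and not an imputation.
- Analyse all randomised patients with outcome data, by assigned arm. Make mean PACU minutes per patient the main summary, with the difference between arms and a bootstrap 95% CI.
- Report stay among PACU patients descriptively (n, median, IQR by arm), with no p-value.
- If a zero-filled Mann-Whitney p-value is reported, say that ties at zero make it largely a repeat of the primary result and that it is not independent evidence.

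The cost is one or two sentences and no new data.
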